In this study, we aim to determine how conscious contents are degraded during anesthetic modification of the conscious state, and to disentangle the causal roles of specific brain areas in state-content interaction through a perturbational approach. We hypothesize that suppressing the state of consciousness will diminish the quality of conscious contents and that this will be associated with functional alterations in three key brain areas: CT, AIC and DLPFC. We also hypothesize that stimulating the three areas will lead to differential perceptual outcomes (e.g., a change in subjective perceptual criterion alone, detection sensitivity alone, or both).

To test the hypotheses, we will (1) administer propofol to reduce the state of consciousness (moderate sedation), (2) perform near-threshold perceptual task to assess the contents of consciousness, (3) apply transcranial low-intensity focused ultrasound pulsation (LIFUP) to noninvasively stimulate the CT, AIC and DLPFC, and (4) perform functional magnetic resonance imaging (fMRI) to measure the related brain process during baseline, sedation, and sedation+LIFUP. We will measure the quality of conscious contents by two orthogonal quantities, criterion (c) and sensitivity (d') derived from the Signal Detection Theory. Here c captures the tendency of a subject to report subjective recognition of a target stimulus regardless of whether the target is present or absent, whereas d' captures the ability of a subject to distinguish between target present and absent trials.

We anticipate that suppressing the conscious state will decrease both c and d', indicating more conservative responses and reduced stimulus differentiation, while c and d' are differentially affected by the activity of DLPFC and AIC. Furthermore, neither c nor d' alone but their product will be associated with the activity of the CT, thus implying a putative mechanism for state-content

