Visual task. Participants will be asked to lay in the scanner, pay attention on the screen, and complete an image recognition task. All stimuli will be programmed using E-Prime (Psychology Software Tools, Pittsburgh, PA) and delivered via a visual presentation system designed for an MRI environment. Stimuli will be presented at the threshold of subjective recognition. An adaptive thresholding procedure will be conducted whereby image contrast will be titrated to reach a 50% subjective recognition rate for each subject. Stimuli will include two common visual object categories: faces and houses. Participants' task is to report the category ("F" or "H") of an image presented and their recognition experience ("Yes" or "No") (Fig. 3). Specifically, they will be instructed to report the object category regardless of their recognition experience and, in cases of unrecognized images, to make a genuine guess (two-alternative choice discrimination). Then, they will be instructed to report whether they see an object, such that even if the object appears unclear or noisy, they should respond "yes", but if they see nothing or only low-level features, such as cloud-like abstract patterns, they should respond "no".

**Fig. 3.** Visual task design. During each 30-min session, participants will complete an image recognition task. Stimuli (faces, houses, and scrambled images) will be presented at the threshold of subjective recognition. Participants' task is to report the category ("F" or "H") of the image presented and their recognition experience ("Yes" or "No").

The stimulus set will include real and scrambled images, where the scrambled images will be created by phase-shuffling a randomly chosen real image from each category to preserve category specific low-level image features [28]. Because scrambled images do not include an object stimulus, they are used as "catch trials" to determine the subjects' baseline tendency to give positive responses to a question about their recognition experience. Each object category will include four unique real images and one scrambled image. Each image will be repeated 10 times (i.e., trials) for each 30-min session. The pre-stimulus interval will vary randomly from trial to trial between 4 and 8 seconds to prevent stimulus timing predictability. The stimuli will be presented in a randomized order to prevent category predictability.

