**Primary Outcome Measure:** Blood Oxygen Level Dependent (BOLD) response to visual stimuli (timeframe: baseline to 90 minutes).

**Secondary Outcome Measure:** Perceptual criterion (c) and sensitivity (d') derived from the Signal Detection Theory (SDT) (timeframe: baseline to 90 minutes).

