# **Data Analysis and Statistics**

For each 30-min session, we will calculate SDT metrics of sensitivity (d') and criterion (c) using subjective reports of recognition as "yes" or "no". The d' indicates the ability to discriminate between real and scrambled images. It is computed by subtracting the z-transformed False Alarms Rate (FAR) from the z-transformed Hit Rate (HR): d' = Z(HR) - Z(FAR)), where Z is an inverse normal cumulative distribution function. The c represents the tendency to make "yes" reports to indicate recognition, regardless of whether the stimulus is a real or a scrambled image, which is computed as:  $c = 0.5 \times (Z(HR)+Z(FAR))$ . We will also calculate percent of correct responses as an operational measure of two alternative-forced-choice sensitivity using subjective category reports, i.e., responses to the first question: "Face" or "House".

For fMRI data, preprocessing steps will be implemented in AFNI (http://afni.nimh.nih.gov/afni). 1) Slice timing correction; 2) Rigid head motion correction/realignment within and across runs; frame-wise displacement (FD) of head motion was calculated using frame-wise Euclidean Norm (square root of the sum squares) of the six-dimension motion derivatives. A frame and its each previous frame will be tagged as zeros (ones, otherwise) if the given frame's derivative value has a Euclidean Norm above FD=0.5 mm; 3) Coregistration with high-resolution anatomical images; 4) Spatial normalization into Talairach stereotactic space and resampling to 3 × 3 × 3 mm³; 5) using AFNI's function 3dTproject, the time-censored data will be high-pass filtered above 0.008 Hz. Undesired components (e.g., physiological estimates, motion parameters) will be removed via linear regression. The latter include linear and nonlinear drift, time series of head motion, its temporal derivative, and mean time series from the white matter and cerebrospinal fluid; 6) Spatial smoothing with 6 mm full-width at half-maximum isotropic Gaussian kernel; 7) The time-course per voxel of each run will be normalized to zero mean and unit variance, accounting for differences in variance of non-neural origin (e.g., distance from head coil).

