We will calculate the average BOLD activity (across the trials with real images) in the regions of interest including the CT, AIC, and DLPFC. For a given measurement, repeated-measures ANOVA plus post-hoc tests will be performed at the group level. Inter-subject multivariate linear regression analyses will be performed with SDT metrics as dependent variables and average BOLD activity as independent variables. Statistical significance will be defined at FDR-corrected  $\alpha < 0.05$ .

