# **Anticipated Results and Interpretation**

We expect to observe a decrease of both c and d' during sedation, indicating more conservative responses and reduced stimulus differentiation. This would suggest that suppressing the state of consciousness diminishes the quality of conscious content. We also expect to find an overall reduction of average BOLD activity across all examined regions, i.e., in CT (state control), AIC (content gating) and DLPFC (content broadcasting). Furthermore, the change of c (baseline vs. sedation) may be associated with the change of DLPFC's average BOLD activity, and the change of d' may be associated with the change of AIC's average BOLD activity. The change of c × d' may be associated with the change of CT's average BOLD activity. Because the activity of CT supervenes on the activity of DLPFC and AIC, the state (CT) and contents (DLPFC/AIC) are altered together in sedation. If found, the results would suggest a neural mechanism for the linkage between state and contents. We also anticipate that the LIFUP stimulation in DLPFC during sedation will increase c without changing d' and increase the average BOLD activity in the

DLPFC. Stimulation of the AIC will increase d' without changing c, possibly through an enhancement of salience/attentional process offsetting the general inhibitory effect of propofol. Importantly, stimulation of the CT is expected to substantially increase both d' and c, arguably restoring perceptual performance to baseline level. This may be accompanied by an overall increase of average BOLD activity along the entire visual processing pathway.

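### The regional BOLD average pools recognised and unrecognised images, so its association with c or d' cannot by itself be attributed to a regional mechanism; a supporting analysis by recognition status would help

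*Combined protocol and SAP*

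**What the plan says.** The primary outcome (Experimental Design) is the "Blood Oxygen Level Dependent (BOLD) response to visual stimuli". Data Analysis and Statistics makes it operational: "We will calculate the average BOLD activity (across the trials with real images) in the regions of interest", namely CT, AIC and DLPFC. Sessions and groups are then compared by repeated-measures ANOVA, and "Inter-subject multivariate linear regression analyses will be performed with SDT metrics as dependent variables and average BOLD activity as independent variables".

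The visual task (Experimental Design) sets the threshold so that "image contrast will be titrated to reach a 50% subjective recognition rate for each subject". Participants report a category and then whether they recognised an object. The analysis section uses the recognition report only to form the hit rate (HR) on real images and the false-alarm rate (FAR) on scrambled ones, and from these d' = Z(HR) − Z(FAR) and c = 0.5 × (Z(HR) + Z(FAR)).

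Anticipated Results and Interpretation expects c, d' and regional BOLD all to fall under sedation. It adds that "the change of c (baseline vs. sedation) may be associated with the change of" DLPFC activity, and pairs d' with AIC and c × d' with CT. If found, these results are to be taken as suggesting a neural mechanism that links state and contents.

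No section separates BOLD by recognition report, adjusts it for hit rate, or says how unanswered trials are handled.

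**The concern.** The BOLD average is taken over exactly the trials whose share of yes reports is the hit rate. If a region responds differently to recognised and unrecognised images, the average depends on the mix of the two kinds of trial as well as on the response to each. Sedation is expected to lower the hit rate, so the average can fall although the response to each kind of trial is unchanged. Because Z(HR) enters both c and d', the same shift also makes the BOLD change correlate with both.

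The plan's own theory makes such a gap plausible: it gives AIC the role of gating conscious access and DLPFC that of broadcasting what becomes reportable. At stake is the mechanistic reading. A region that merely follows recognition could show both the sedation fall and an association with c or d', and so look like one that gates or broadcasts.

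**Working it through.** **Inputs from the documents (visual task; analysis section).** Real-image trials per session: 2 categories × 4 images × 10 repeats = 80. Scrambled trials: 2 × 1 × 10 = 20. Target HR awake: 0.50. The formulas for c and d' are as above. The documents give no sedated HR, FAR, trial noise or recognised/unrecognised gap, so there is no plan figure to reproduce here. Everything below uses assumed values for these.

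**Step 1: identity.** With B(rec) and B(unrec) the mean responses to answered real trials of each kind,

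mean BOLD = HR × B(rec) + (1 − HR) × B(unrec).

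Set B(rec) = 1 and B(unrec) = r, both unchanged by sedation, and let HR fall from 0.50 to 0.30 (assumed).

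- r = 1: no change.
- r = 0.75: 0.825 / 0.875, a fall of 5.7%.
- r = 0.5: 0.65 / 0.75, a fall of 13.3%.
- r = 0.25: 0.475 / 0.625, a fall of 24%.
- r = 0: 0.30 / 0.50, a fall of 40%.

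**Step 2: effect on c and d'.** With FAR fixed, Δd' = ΔZ(HR) and Δc = 0.5 × ΔZ(HR). Here Z(0.30) − Z(0.50) = −0.52, so d' falls by 0.52 and c by 0.26. Both move with the quantity that moves the BOLD average.

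**Step 3: simulation of hit-rate mixing.** The response to each kind of trial is held constant from baseline to sedation. Assumptions: mean change in Z(HR) −0.5 with between-subject SD 0.5; FAR about 0.15, its change on the Z scale having SD 0 or 0.5; single-trial noise SD 1; gap in units of that SD; tests at unadjusted 0.05. Ranges cover the two FAR settings.

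| Gap | Correlation of BOLD change with Δc and with Δd' (each) | False sedation effect, 25 subjects | False sedation effect, 100 subjects |
|---|---|---|---|
| 0 | 0.00 | 4–6% | 5–7% |
| 0.25 | 0.17–0.20 | 24% | 71–77% |
| 0.5 | 0.30–0.37 | 58–62% | 100% |
| 1.0 | 0.46–0.56 | 90–93% | 100% |

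In the same runs, a mean over recognised trials only gave correlations of about 0.00 and a false sedation effect in 4–7%. With 25 subjects, exactly one of the two correlations was significant in 23–51% of runs at gaps 0.25 to 1.0, against 10% with no gap. The c × d' association planned for CT was not simulated.

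**Step 4: the opposite case.** Suppose instead that BOLD follows graded evidence, which the subject cuts at a criterion, and that sedation only moves the criterion (HR from about 50% to 27%, between-subject SD of the shift 0.5, at least 5 trials per class, 25 subjects). The neural response does not change. The all-trials average then shows a false session effect in about 5% of runs. An equal-weight mean of the two class estimates shows one in about 99%, 93–95% and 55–56% at trial noise SD 1, 2 and 4 evidence units, and correlates with Δc at −0.65, −0.49 and −0.29. The classes are selected by a criterion that has itself moved.

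**The case against.** The strongest defence is that the all-trials average is a sound estimand. The primary outcome is the response to visual stimuli, and averaging over all real images gives the total effect of sedation or LIFUP on it. For LIFUP against sham it keeps the randomised comparison. Recognition is a response made after the intervention, so analysing within recognition class conditions on an outcome; Step 4 shows that this can be badly biased in the case the plan itself expects, more conservative responding under sedation. And if gating is all-or-none, its whole effect is to move trials from unrecognised to recognised. A rule that the effect must hold within class would then reject the very mechanism under study. All of this stands. It rules out replacing the primary measure and rules out such a requirement.

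Three stronger readings are tempting and not supported.

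- A reader might infer that the BOLD results cannot be interpreted at all. The total effect can be; only its attribution to a regional mechanism is open.
- A reader might infer that mixing would manufacture the predicted dissociation (DLPFC with c, AIC with d'). In expectation it gives near-equal correlations with both. What remains is that one significant and one non-significant correlation would be weak evidence, since Step 3 produces that pattern often at 25 subjects.
- A reader might infer that unanswered trials are inside the average. The plan is silent on them.

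It is also fair that the size rests on assumed inputs, and that the simulated tests are unadjusted whereas the plan specifies FDR correction.

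**Conclusion.** The point holds in a limited form. The planned average mixes two kinds of trial in proportions set by the hit rate, and the hit rate also drives c and d'. If recognised images evoke the larger response, a fall in hit rate alone lowers the average and correlates it with both metrics, so the predicted associations do not by themselves identify a regional mechanism.

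The size is conditional: nothing with no gap, and correlations of about 0.2 to 0.6 for gaps of 0.25 to 1 single-trial SD under the assumptions of Step 3. The documents do not say where in that range the trial lies. The randomised LIFUP-versus-sham comparisons of c and d' do not use BOLD and are unaffected.

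Neither measure is safe alone. The all-trials average is open to hit-rate mixing, and class-specific means are open to selection when the criterion shifts. Because they fail under different conditions, reporting both improves attribution. This is a cheap improvement, not a fault that invalidates the primary outcome.

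**What to change.** 1. Keep the all-trials average as the primary, total-effect measure.
2. Add separate first-level regressors for recognised real, unrecognised real, scrambled and unanswered trials. Take the all-trials average from its existing calculation; an overall real-image regressor in the same design matrix would duplicate the sum of the real-trial classes.
3. Pre-specify the recognised and unrecognised estimates, each reported with a stated minimum trial count per class, as a supporting analysis for the session and group comparisons and for the regression on c and d'.
4. State that a BOLD–c or BOLD–d' association will be read as a regional mechanism only after considering both results, and name the weakness of each: hit-rate mixing for the average, selection by a shifted criterion for the class means.
5. Do not substitute the equal-weight class mean for the primary measure, and do not require an effect to hold within class.

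The cost is SAP wording and a little more analysis; no new data, scans or subjects are needed. The downside is precision under sedation. At an assumed HR of 25%, about 20 of 80 real trials are recognised and 60 are not, so with equal trial noise the standard error of the recognised-trial mean is √(80/20) = 2 times that of the all-trials mean. Some subjects may miss the minimum count.

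### BOLD is averaged over real-image trials only, so the content interpretation and the d' regression rest on a measure that is not content-specific; a real-minus-scrambled contrast should be prespecified beside it

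*Combined protocol and SAP*

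**What the plan says.** All references are to the combined protocol and SAP.

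- **Primary outcome** (end of Experimental Design): "Blood Oxygen Level Dependent (BOLD) response to visual stimuli". No contrast or control condition is named.
- **Analysed measure** (Data Analysis and Statistics): "We will calculate the average BOLD activity (across the trials with real images) in the regions of interest including the CT, AIC, and DLPFC". This average enters a repeated-measures ANOVA and is the predictor in inter-subject regressions with the SDT metrics as outcomes.
- **Sensitivity** (same section): "The d' indicates the ability to discriminate between real and scrambled images". It is computed as Z(HR) - Z(FAR).
- **Scrambled trials** (Experimental Design, Visual task): "Because scrambled images do not include an object stimulus, they are used as" catch trials, to measure the tendency to answer yes. They are made by "phase-shuffling a randomly chosen real image from each category to preserve category specific low-level image features". On numbers: "Each object category will include four unique real images and one scrambled image", with 10 repeats of each image per session.
- **Interpretation** (Anticipated Results and Interpretation): AIC activity is labelled as gating and DLPFC activity as broadcasting of content. The change in d' is linked to the change in average AIC activity.

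Nowhere does the plan specify a BOLD contrast of real with scrambled images, of recognised with unrecognised trials, or any other task control.

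**The concern.** Every trial, real or scrambled, includes a visual onset, a forced face/house choice and a yes/no report. An average over real-image trials contains the activity for all of these as well as any activity due to the object. The planned preprocessing removes drift, motion, white-matter and CSF signal, but nothing tied to the task itself.

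Propofol or LIFUP could change general visual drive, decision making or responding. Such a change would move the real-only average, and under the stated interpretation it could be reported as a change in the gating or broadcasting of contents. The d' regression has a related gap: d' depends on behaviour in the scrambled trials, while its BOLD predictor uses no data from them.

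**Working it through.** The plan gives no figure for content specificity, so there is none to reproduce. The checks below use its trial counts, its SDT formulas and, for the cost of the contrast, its effect size.

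**1. Trials per session.** Real: 2 categories x 4 images x 10 = 80. Scrambled: 2 x 1 x 10 = 20. Scrambled trials are 20 of 100.

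**2. How d' depends on the scrambled trials.** At HR = 0.50 (the titration target), Z(HR) = 0 and d' = -Z(FAR):

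| FAR | d' |
|---|---|
| 0.05 | 1.64 |
| 0.20 | 0.84 |
| 0.50 | 0.00 |

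With behaviour on real images fixed, d' can move across this range through scrambled trials alone.

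**3. What the real-only average can pick up.** Assume the real-image response is G + C, where G is common to all trials and C is object-related, and that the scrambled response is G. The documents give neither part.

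- If G falls by 20% and C is unchanged, the real-only average falls by 0.20 x G/(G + C). For G at 80%, 50% or 20% of the response this is 16%, 10% or 4%. Real minus scrambled equals C and does not change.
- If G and C vary independently between subjects, the correlation of real-only BOLD with C is 1/sqrt(1 + var(G)/var(C)). For variance ratios of 0.25, 1 and 4 this is 0.89, 0.71 and 0.45.

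**4. Precision of the contrast.** In units of single-trial variance, the real-only mean has 1/80 = 0.0125 (SE 0.11). Real minus scrambled has 1/80 + 1/20 = 0.0625 (SE 0.25). The ratio is 5 in variance and 2.24 in SE.

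**5. What that could do to power.** The Power Analysis section gives d = 0.56, 80% power, alpha 0.05 and N = 24, without naming the test or sidedness. A two-sided normal calculation for a within-subject comparison gives ((1.960 + 0.842)/0.56)^2 = 25.03, so 26; a two-sided paired t-test gives 28. The stated 24 is near these and is not disputed here.

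Assume that 0.56 applies to the real-only session difference, that the contrast has the same raw effect, and that a share f of the variance of that difference is trial noise (f is not in the documents). The contrast then has d = 0.56/sqrt(1 + 4f). For a two-sided paired t-test:

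| f | d | power, n = 25 | N for 80% |
|---|---|---|---|
| 0 | 0.56 | 77% | 28 |
| 0.10 | 0.473 | 62% | 38 |
| 0.25 | 0.396 | 48% | 53 |
| 0.50 | 0.323 | 34% | 78 |

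The n = 25 column applies to comparisons within one LIFUP group. A baseline-to-sedation comparison pooling all 100 evaluable subjects would exceed the required N in every row. If between-subject variance shared by both trial types cancels in the subtraction, the loss is smaller.

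**The case against.** **The primary outcome is satisfied.** It is worded as a response to visual stimuli, and a real-image average fits that. This stands. The point concerns the interpretation and the d' regression, not the definition of the primary outcome.

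**The design already has controls.** Each subject is compared across sessions, LIFUP groups are randomised against sham, and the interpretation depends on a pattern: associations with changes in c, d' and c x d', and different effects by stimulated region. A non-specific response alone would not produce that pattern, so a reader should not infer that any visually responsive region would pass as tracking contents. But these features control for time and sedation. They do not show which part of the response moved.

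**Scrambled trials are an imperfect control.** They are rarer (20%) and less varied (one image per category against four), and their rate of yes reports need not match the 50% targeted for real images. The contrast therefore also carries rarity and report effects, and it averages recognised with unrecognised real trials. This stands, and is why the contrast should support the real-only measure and not replace it.

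**A predictor need not mirror its outcome's arithmetic.** True. The mismatch is clearest for d'. For c, which the plan computes from the sum of Z(HR) and Z(FAR), subtraction is not the natural counterpart.

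**Conclusion.** The concern holds for the content interpretation and the d' regression. As planned, neither can distinguish a change in object-related activity from a change in activity common to all trials. The size of any bias cannot be computed from the documents; the 4% to 16% falls and the correlations of 0.45 to 0.89 rest on assumed splits and show only the kind of error possible.

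A reader might go further and argue that preprocessing step 7 ("The time-course per voxel of each run will be normalized to zero mean and unit variance") makes the predicted overall reduction unobservable. With a run mean of zero, 0.8 x real + 0.2 x scrambled = 0, so the real-trial mean would equal one fifth of the real-minus-scrambled difference. That requires trial windows that together cover the whole run, and the plan states no window. In an illustrative zero-mean run (100 trials, 18 s apart, standard response shape, no unit-variance scaling), real and scrambled amplitudes falling from 1.0 and 0.5 to 0.6 and 0.1 leave a full-trial average at 0.03. In a 3-9 s window the average falls from 0.51 to 0.32, so the reduction is visible. The documents do not support the stronger claim.

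The change is advisable and modest: the primary outcome stands, while the claims about contents need the added contrast.

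**What to change.** 1. Keep the real-only average as the measure for the primary outcome.
2. For each ROI and session, estimate real-image and scrambled-image responses in one event-related model, and report both.
3. Prespecify real-minus-scrambled as a supporting measure reported alongside. Run the d' regression with it as well as with real-only BOLD.
4. Describe an effect as content-specific only if the contrast supports it; otherwise describe it as a change in the response to visual stimuli.
5. State the limits in the SAP: the contrast has 5 times the trial-noise variance, and scrambled trials are rarer, less varied and may differ in yes-report rate. A null contrast is therefore not evidence against a content effect.

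The cost is SAP wording and analysis time. The scrambled trials are already planned, so no added scanning or participants are needed. The price is low precision for the contrast within a group of 25, which is why it should be supporting.
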